## 1.0 Objectives

The overarching goal of this proposal is to understand the comparative effectiveness of obesity counseling as covered by Centers for Medicare and Medicaid Services (CMS) in improving weight loss for adults either with or at high risk of type 2 diabetes. CMS and most insurers now include obesity screening and counseling benefits, with no cost sharing to patients. Since overweight patients are at highest risk for diabetes, improved weight management services could prevent diabetes and its negative health outcomes. Beneficiaries with obesity are eligible for up to 20 face-to-face visits for weight counseling in the primary care setting. We propose comparing weight and diabetes outcomes in three states using electronic health record (HER) and claims data before and after this policy was implemented. The PaTH network brings together six academic health systems – the University of Pittsburgh/University of Pittsburgh Medical Center, Penn State College of Medicine/Hershey Medical Center, Temple University School of Medicine/Temple Health, and the Johns Hopkins University/Johns Hopkins Health System/Johns Hopkins Health Care, Geisinger Health Systems, and The University of Utah – to function as an integrated research network and learning health system, providing an infrastructure for observational studies, such as the one proposed here, that require populations beyond a single health system to answer important patient-centered health services questions ([www.pathnetwork.org](http://www.pathnetwork.org)). Using the PaTH Clinical Data Research Network (CDRN) infrastructure, we propose the following specific aims:

**Aim 1: Evaluate the impact of universal preventive service coverage for obesity screening and counseling on weight loss, diabetes incidence, and diabetes outcomes, in patients with diabetes or at high risk for diabetes (defined by body mass index (BMI)  $\geq 25$ ).** We will determine how the annual probability of receiving obesity and/or nutritional counseling (as defined by Current Procedural Terminology (CPT) code) changed pre- and post-policy across all insurers in a cohort of patients with diabetes and at high risk for diabetes. We hypothesize that individual patients are more likely to receive counseling following coverage implementation. Further, we hypothesize that patients who receive a greater number of face-to-face visits will have greater weight loss compared to those who receive fewer visits.

**Aim 2: Compare patient weight loss and diabetes-related outcomes among those who receive obesity screening and counseling to those who do not, following implementation of preventive service coverage.** We will examine post-policy impact of obesity screening and counseling in a cohort of patients with diabetes and at high risk for diabetes. Specific outcomes to be examined include weight loss, diabetes incidence, and diabetes outcomes (including hemoglobin A1c, controlled blood pressure, use of a statin medication). Further, we will determine patient characteristics, including demographics (age, race/ethnicity, rurality), and practice characteristics, including provider type, and their impact on receiving/providing obesity screening and counseling. Understanding patient and practice characteristics most likely to engage in obesity counseling can identify best practices and inform how to increase engagement by both patients and providers.

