## 2.0 Background

### 2.1 Scientific Background and Gaps

Overweight and obesity are America's number one health concern. The prevalence of obesity in the US is greater than 36%, which is far above the Healthy People 2020 objective of less than 30.5%. Perhaps most concerning is the rate that obesity has increased, having doubled since 1970. As the second most preventable cause of death, obesity is a risk factor for diabetes, cardiovascular disease, stroke, and cancer, all major causes of death in the US. Addressing obesity through lifestyle interventions decreases the risk of developing type 2 diabetes, a disease which affects over 29 million people (9.3% of the US population). Diabetes is associated with serious complications, including cardiovascular disease, blindness, renal failure and lower extremity amputation. Although complications are preventable with proper medical and lifestyle management, including weight loss, nearly half of patients with diabetes do not have adequate glycemic control.

Primary care clinics may be an ideal setting for weight control interventions. Greater than 80% of Americans see a PCP regularly and access to primary care is expected to increase with health care reform. Further, as PCPs identify and treat the multitude of conditions affected by being overweight, including diabetes, they are ideally positioned to best engage their patients in weight management. The Centers for Medicare and Medicaid Services (CMS) implemented a healthcare procedure coding system code for intensive behavioral therapy (IBT) for obesity within primary care settings in 2012 to facilitate payment for addressing obesity, which was followed by universal coverage by insurers for IBT for adults of all ages in 2013. However, the impact of this coverage on patient-centered outcomes is largely unknown.

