***Diabetes Cohort Definition.*** During year 1 of the proposed project, the investigative team, in collaboration with the PaTH Network, will identify a valid cohort of patients with type 2 diabetes. The cohort of patients under study will be defined as all patients age 18 and older with an indication of type 2 diabetes during the proposed study time frame. Patients will be classified as having diabetes using a clinically validated algorithm: type 2 diabetes mellitus on the problem list, diabetes-specific medications, hemoglobin A1c (HbA1c) results > 7.0%, or one inpatient diagnosis code or two outpatient diagnosis codes for type 2 diabetes (ICD-9 codes 250.xx). The diabetes cohort will be further limited to patients who will likely be captured in the PaTH EHR records or claims data so that outcome assessments can occur. Thus, we will further limit the diabetes cohort to patients who have either: (1) had at least 2 outpatient primary care visits in one of the PaTH health systems in the past 3 years (since January 1, 2012), or (2) for whom claims data are available. The cohort will be dynamic, with new patients added into the cohort after 2015 as they meet the diabetes cohort definition prospectively. The observational period for the outcome variables will be for the 10-year period from 2009-2019, thus including 3 years of data prior to the first policy change (CMS instituting coverage for intensive behavioral therapy for obesity) and 3 years after the last policy change (Pennsylvania Medicaid expansion) under study.

Following the definition of the diabetes cohort and key diabetes outcomes and covariates as described above, an initial extraction of variables will be conducted in Year 2 of the proposed project for years 2009-2015. This early data extraction from the PaTH Network will allow for cohort validation and data cleaning and editing, as well as required programming and determination of the analysis models. We will utilize this initial data extraction in Years 2 and 3 to analyze the impact of early health policy changes, as well as to prepare a manuscript of both the protocol and early findings of policy impact. The final data extraction will occur during the final quarter of Year 4 of the proposed project, allowing for completion of a ten-year time period (2019).

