## 8.0 Statistical Plan

Descriptive statistics will be generated to describe the characteristics of different cohorts of interest. The diabetes related outcomes will be summarized at the individual level on a yearly basis. There will be binary outcomes (Yes/No) such as controlled diabetes, controlled blood pressures, receiving annual eye exam, receiving obesity and/or nutritional counseling, and count outcomes such as numbers of clinic visits, emergency department visits and hospitalization, and continuous outcomes such as cost of healthcare utilizations. The distributions of outcome measures will be examined by using minima, maxima, ranges, medians, quartiles, means, and standard deviations for continuous variables, and frequency and contingency tables for categorical variables.

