To evaluate the impact of policy changes on these outcomes, we will examine how these outcomes change over time, in response to the policy changes. As descriptive analyses, we will plot the mean trajectory of each yearly outcome at clinic level, health system level and state level. The statistical modeling of patterns of changes in individual level outcomes will be carried out through multi-level mixed-effects models. The mixed-effects model is a common and popular modeling technique for longitudinal data. A mixed-effects model can accommodate within- and between-subjects variability, as well as serial correlations. In addition, it has the flexibility to incorporate time-dependent covariates, incomplete data, and heteroscedasticity of the variances and correlations. The mixed-effects model will be specified in a multi-level fashion so that different levels of variability (e.g., individual characteristics, social environment, built environment) can be taken into account. The pattern of changes in the outcome will be assessed for pre- and post-periods, respectively, based on the piecewise/segmented regression models. The slope of each segment indicates the trend of change in diabetes outcome in that period. Therefore, the change in the trend/slope post-policy implementation may reveal the actual impact of the new policy controlling for baseline level and trend. Such modeling strategies share the same spirit of interrupted time series analysis. While the classical interrupted time series design often generates a single long series of data, we have a large number of short series from each individual subject, namely, longitudinal data. Depending on the types of the outcomes, we will specify mixed-effects models based on logistic

regression for a binary outcome, Poisson regression for a count outcome and linear regression for a continuous outcome as detailed below.

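### Aim 1 measures counseling uptake by billing code, but the IBT code dates only from 2012; if it is in the outcome set, coding and delivery cannot be told apart

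*Combined protocol and SAP*

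**What the plan says.** Section 1.0, Aim 1, sets the uptake question as how the "annual probability of receiving obesity and/or nutritional counseling (as defined by Current Procedural Terminology (CPT) code) changed pre- and post-policy", across all insurers. Its hypothesis is "We hypothesize that individual patients are more likely to receive counseling following coverage implementation". Section 8.0 lists this among the yearly individual-level binary outcomes ("receiving annual eye exam, receiving obesity and/or nutritional counseling, and count outcomes").

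Section 2.1 says that CMS "implemented a healthcare procedure coding system code for intensive behavioral therapy (IBT) for obesity within primary care settings in 2012 to facilitate payment", and that this was "followed by universal coverage by insurers for IBT for adults of all ages in 2013".

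Section 7.2 sets the observation period at 2009-2019, so that it includes "3 years of data prior to the first policy change (CMS instituting coverage for intensive behavioral therapy for obesity"). By the protocol's own account, the IBT code was not in use in 2009-2011.

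Section 8.0 reads the policy effect from a segmented mixed model: "the change in the trend/slope post-policy implementation may reveal the actual impact of the new policy controlling for baseline level and trend". The two segments are joined at the time origin and there is no term for a jump in level.

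The documents do not list the counseling codes or the years in which each was available. They plan no check of codes against clinical notes and no analysis restricted to codes available throughout.

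**The concern.** The 2012 step changed what could be paid for and, at the same time, what could be recorded. If the IBT code is in the outcome set, it is necessarily absent in the first three data years and available afterwards. Counseling that was given before 2012 but not coded, or coded outside the set, could then enter the outcome without any change in care.

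The hypothesis is about patients receiving counseling. A change in coded counseling answers it only if the share of delivered counseling that gets coded stays stable, and the plan offers no way to check this. Covariate adjustment and the propensity-score analysis in section 8.0 balance patient characteristics. They do not correct an outcome whose recording shifts with calendar time.

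The wording also leaves the outcome set open. Aim 1 refers to Current Procedural Terminology, while section 2.1 refers to a healthcare procedure coding system code. If the IBT code is in, the recording problem arises. If it is out, the uptake outcome omits the service whose coverage is being studied.

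**Working it through.** The plan states no uptake rate, so there is no figure to reproduce. The check is an illustration of direction and possible size.

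**Inputs from the documents**
- IBT code 2012, universal coverage 2013 (section 2.1); data 2009-2019 (section 7.2).
- Model: log odds linear before and after t = 0, joined at t = 0 (section 8.0).
- Time origin: 2014 is stated for Utah in the ACA model. The post-coverage analysis uses t = 0 to 6, and 2019 - 6 = 2013. The year 2012 is added because the code dates from then.

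**Assumptions, not in the documents**
- Delivered counseling p is constant at 5% or 10% of patients per year.
- The coded share is s0 before 2012 and s1 from 2012.

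**Simple pre/post comparison.** Coded rate = p × s, and OR = [p·s1/(1 - p·s1)] / [p·s0/(1 - p·s0)]. For p = 0.10, s0 = 0.10 and s1 = 0.50: (0.05/0.95)/(0.01/0.99) = 0.05263/0.01010 = 5.21.

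**Segmented model.** The fixed-effects part of the section 8.0 model was fitted to the same yearly rates, with years weighted equally and random effects left out. Slope change = post-slope minus pre-slope, in log odds per year, shown for p = 0.10.

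| Coded share | OR (p = 5%; 10%) | Origin 2012 | Origin 2013 | Origin 2014 |
|---|---|---|---|---|
| 20% to 40% | 2.02; 2.04 | -0.273 | -0.224 | -0.189 |
| 10% to 30% | 3.03; 3.06 | -0.458 | -0.355 | -0.286 |
| 10% to 50% | 5.10; 5.21 | -0.728 | -0.519 | -0.399 |

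At p = 5% the slope changes are nearly the same; the smallest is -0.186. The sign is negative because the segments must meet at the origin, so a step at or before it tilts the pre-period line upward. For 10% to 50% with origin 2012, the pre-slope is 0.743 and the post-slope 0.016.

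**Sensitivity of the direction**
- With a four-year phase-in (10% to 50%, p = 10%), the slope changes are -0.358, -0.350 and -0.337 for origins 2012, 2013 and 2014.
- With a slow rise in equal yearly steps from 10% in 2012 to 50% in 2019, they are +0.091, +0.025 and -0.014. The downward bias therefore belongs to a step or a quick phase-in.
- If the coded share does not change, the OR is 1.0 and the slope change is 0.
- With a level-change term at 2012, the pure step gives a slope change of 0 and a level coefficient of 1.651 = ln(5.21).

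**Detectability.** With 320,000 patients per period treated as independent and two-sided 0.05, coded rates of 4.85% and 5% are distinguished with power of about 0.79, and 4% and 5% with power of about 1.0. At p = 10%, the first pair is a coded share moving only from 48.5% to 50%.

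**Codes available throughout.** If half of a 2% coded rate moves to the new code with care unchanged, the older codes show (0.01/0.99)/(0.02/0.98) = 0.495, a false decline.

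**The case against.** A reader might infer that coded counseling must rise at the policy date, so that Aim 1's first hypothesis is true by construction. The documents do not support that, for three reasons.

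- **Inclusion is not established.** The artifact needs the IBT code to be in the set and to capture counseling previously uncoded or coded outside it. The outcome also covers nutritional counseling, for which codes may already have existed in 2009.
- **The dates differ.** The code dates from 2012, but Aim 1 concerns universal coverage, which section 2.1 dates to 2013. The two coincide only for the earlier CMS step.
- **The planned model behaves differently.** Under a 2012 coding step, the section 8.0 slope change moves against the hypothesis. False confirmation is a risk of a simple comparison of probabilities.

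It is also fair that section 2.3 gives uptake of the CMS benefit as part of the rationale. Billed use measures that directly, so total coded counseling is a legitimate outcome. Restricting the main analysis to older codes would remove the benefit under study.

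All of this stands, and it limits the point without removing it. The hypothesis speaks of receiving counseling, and nothing planned separates a change in recording from a change in care.

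**Conclusion.** The concern holds in conditional form. If the 2012 IBT code is in the outcome set, part of any pre/post change in coded counseling may reflect coding. A 2012 coding step would bias a simple pre/post comparison upward and the section 8.0 slope change downward.

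Under the assumed shares, the spurious odds ratio is about 2 to 5 and the spurious slope change -0.19 to -0.73 log odds per year. These illustrate invented coded shares with delivered counseling held constant. They are not estimates for this study, and the effect is zero if the coded share is stable. Given the planned sample, even a small shift could reach statistical significance.

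The gap should be closed before the uptake analysis is interpreted. It does not invalidate coded counseling as a measure of benefit uptake.

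**What to change.** 1. List every counseling code in the outcome, with its coding system and the years it was available. State whether the IBT code is included, and reconcile the wording of Aim 1 and section 2.1.
2. Keep total coded counseling as the measure of benefit uptake.
3. Beside it, report (a) a sensitivity analysis using only counseling codes available in every year 2009-2019, and (b) IBT-code use separately from 2012 on.
4. Conclude that delivered counseling rose only if the total-code and fixed-code results agree. Otherwise describe the result as a change in coded counseling.

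Two optional additions would help: a level-change term at 2012, so that a step is not forced into the slopes, and a check of codes against notes in a sample from before and after 2012. The second matters because payment could also raise the use of older codes, which agreement between code sets would not reveal.

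The cost is a code list and one or two extra models; the notes check would be additional work at the sites. The fixed-code result can understate counseling, or show a false decline if clinicians switch to the new code, so it should not stand alone.

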**Table 1. Proposed Outcomes for the Pre-diabetes and Diabetes Cohorts**

Outcomes	Definition	Notes
Pre-diabetes cohort		
Weight loss during counseling	Weight lost from first IBT visit to final IBT visit	Available at all PaTH sites
Weight loss maintenance	% of weight lost during program and maintained over remaining time period, reported by year	Available at all PaTH sites
Diabetes incidence	% of patients who develop diabetes per year following weight counseling	Available at all PaTH sites
Patient-reported outcomes	-SF-12 -PHQ-2, PHQ-8, PHQ-9 -Physical function -sleep -fruit and vegetable consumption -social support -physical activity -PROMIS (PROMIS 29, physical function, depression) -healthy lifestyles -patient reported medication reconciliation	Available at some sites – Formal inventory of PROs will be collected at each institution at the beginning of the project, to be included as secondary outcomes
Diabetes cohort		
Weight loss during counseling	Weight lost from first IBT visit to final IBT visit	Available at all PaTH sites
Weight loss maintenance	% of weight lost during program and maintained over remaining time period, reported by year	Available at all PaTH sites
Patient reported outcomes	-SF-12 -PHQ-2, PHQ-8, PHQ-9 -Physical function -sleep -fruit and vegetable consumption -social support -physical activity -PROMIS (PROMIS 29, physical function, depression) -healthy lifestyles -patient reported medication reconciliation	Available at some sites – Formal inventory of PROs will be collected at each institution at the beginning of the project, to be included as secondary outcomes
Uncontrolled diabetes	Average A1c > 9 or no A1c	Available at all PaTH sites
Controlled blood pressure	SBP < 140, DBP < 90, averaged across values over year	Available at all PaTH sites
On a statin medication	Evidence of a statin medication on current EHR medication list	Available at all PaTH sites
Receiving annual eye exam	Documentation of eye exam once in past year	Available at all PaTH sites
Receiving annual urinary microalbumin test	Documentation of lab testing for urinary microalbumin at least once in past year	Available at all PaTH sites
Lower extremity amputations	Documentation of procedure for lower extremity amputation or billing code through health plans in past year	Available at all PaTH sites

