Furthermore, we will use the similar models as described above to evaluate post-policy impact of obesity screening and counseling (number of visits) on the outcomes such as weight loss, diabetes incidence, and diabetes outcomes (including hemoglobin A1c, controlled blood pressure, use of a statin medication). The outcome data collected after the universal coverage change (i.e.,  $t = 0, 1, \dots, 6$ ) will be used to estimate the trend of change. The number of screening and counseling will be used as a predictor in the mixed effects models. The effects of patient and practice characteristics will also be examined in the models. Statistical software SAS 9.4 and R environment will be used to implement the proposed analyses.

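### Uptake counts any obesity or nutritional counseling, but weight loss is scored only between IBT visits, so nutrition-only patients count as counseled, have no weight-loss value, and have no stated side in Aim 2

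*Combined protocol and SAP*

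**What the plan says.** The event called counseling is worded differently wherever it is used.

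- **Uptake.** Section 1.0, Aim 1, studies the "annual probability of receiving obesity and/or nutritional counseling (as defined by Current Procedural Terminology (CPT) code") before and after the policy. Section 8.0 lists "receiving obesity and/or nutritional counseling" among the yearly binary outcomes.
- **Weight loss.** Section 7.2, Table 1, gives one definition for both cohorts: "Weight lost from first IBT visit to final IBT visit". Maintenance is the percentage "of weight lost during program and maintained over remaining time period, reported by year", so it depends on the same interval.
- **Diabetes incidence.** In the at-risk cohort, Table 1 uses the percentage "of patients who develop diabetes per year following weight counseling".
- **Aim 2 groups and predictor.** Section 1.0, Aim 2, compares patients who receive obesity screening and counseling with those who do not. Section 8.0 then models the "post-policy impact of obesity screening and counseling (number of visits") on weight loss, diabetes incidence and diabetes outcomes.
- **The covered service.** Section 2.1 says that CMS introduced a code for "intensive behavioral therapy (IBT) for obesity within primary care settings in 2012". Observation starts in 2009 (Sections 7.1 and 7.2).

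No section lists the codes, equates these terms, or says where a patient with nutritional counseling only belongs.

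**The concern.** Aim 1 joins two hypotheses: coverage makes counseling more likely, and more face-to-face visits bring more weight loss. The first is tested on everyone with obesity or nutritional counseling. The second, under Table 1, can be tested only on patients with IBT visits. The two results would then describe different patients, yet be read as steps in one chain.

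Aim 2 has a related gap. Its split into received and not received is exhaustive, so a nutrition-only patient must go on one side, and the choice is left open. On the counseled side the patient has no Table 1 weight loss. On the other side, a patient whom Aim 1 counts as counseled sits in the uncounseled comparator. If this is settled only after extraction, the assignment can be made with results in view.

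**Working it through.** The documents state no figure to reproduce, and the power paragraph gives no inputs. The check applies the definitions to each type of patient.

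| Patient | Aim 1 uptake | Table 1 weight loss | Aim 2 side |
|---|---|---|---|
| Two or more IBT visits | Yes | Defined | Received |
| One IBT visit | Yes | First visit is also the final visit, so no usable change | Received |
| Nutritional counseling only | Yes | None: no IBT visit | Not stated; can be not received |
| Never counseled | No | None: no IBT visit | Not received |

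The first two rows assume that the IBT code is among the uptake codes. Without a code list the documents do not confirm this.

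**Row three** is the conflict between the stated rules. **Row four** shows that it is part of a wider gap: the Aim 2 comparator has no weight-loss value under Table 1.

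**Can such patients arise under the eligibility rules?** Yes.

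- Section 1.0 describes the benefit as being for beneficiaries with obesity, while the at-risk cohort starts at BMI 25. The table in Section 7.2 puts 944,655 of 2,062,499 at-risk patients at BMI 25-29.9: 944,655 / 2,062,499 = 46%. (The 32% printed in that row implies a larger denominator.) Taking obesity as BMI 30 or more, which is an assumption because the documents give no cut-off, these patients fall outside the benefit as described. Any nutritional counseling they receive still counts as uptake.
- The diabetes cohort has no BMI criterion.
- Before 2012 the IBT code did not exist, so uptake in 2009-2011 can rest only on other codes. Patients counseled only in those years have no Table 1 weight loss.

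This shows that the group can exist. It does not show how large it is.

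**Size, by assumption.** Let s be the nutrition-only share of patients counted as uptake.

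- Share counted as uptake with no weight-loss value for this reason = s. For s = 10%, 30% or 50%, that is 10%, 30% or 50%.
- Suppose these patients are placed in the Aim 2 counseled group, have an outcome that is defined for them (HbA1c, for example), and gain nothing from their counseling. The group's mean effect is then (1 - s) times the IBT effect: 90%, 70% or 50% of it.
- Suppose instead they make up a fraction c of the comparator and gain a fraction f of the IBT effect. The contrast is then (1 - c × f) times the IBT effect. The documents give neither c nor f. If nutrition-only patients are few beside all uncounseled patients, c is small and so is this bias.

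**The case against.** The strongest reply is that the broad uptake definition is deliberate and right. A pre/post question needs codes that could be recorded in both periods, and by code IBT is zero before 2012. An IBT-only contrast would rise by construction, recording the creation of a billing code and not a change in care. This stands: the broad outcome should be kept, and an IBT-only contrast cannot carry the policy claim. It does not explain why weight loss, visit count and Aim 2 grouping fail to follow the same definition.

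Other parts of the reply also stand.

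- A reader might infer that a rise in nutritional counseling unrelated to coverage would be reported as policy uptake. The segmented model in Section 8.0 estimates separate slopes before and after the policy, so a steady drift would largely be carried by the earlier slope. Only a change of trend that coincides with the policy would be misattributed.
- A reader might infer that nutrition-only patients have no group at all in Aim 2. The split is exhaustive; what is missing is the side.
- The label used in Aim 2 is also the one Section 1.0 uses for the covered benefit, so it does not by itself prove a third scope.

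It could also be said that Section 8.0 works with yearly measurements, so yearly weights might be modeled for everyone. The framework allows it, but no section defines such an outcome; the only weight-loss definitions are those in Table 1.

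**Conclusion.** The concern holds as a conflict between stated rules. Patients with nutritional counseling only count as Aim 1 uptake, have no weight-loss value under Table 1, and have no stated side in Aim 2, where they can enter the uncounseled comparator. The never-counseled patients whom Aim 2 needs for comparison also have no Table 1 weight loss.

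The size is unknown. The 10% to 50% range is illustration only. A reader might go further and infer that most of the counted counseling was not the covered service. That would need rates of nutritional counseling and IBT, and the documents give none.

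The conclusion rests on reading Table 1 and the two aims as written. A code list elsewhere that treats nutritional counseling visits as IBT would remove the conflict for nutrition-only patients, but not the gap for the never-counseled. The point should be settled before the outcome data are analyzed; it does not invalidate the design.

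**What to change.** 1. **Code list and flag.** List the counseling codes, and flag each encounter as IBT for obesity or as other obesity or nutritional counseling.
2. **Uptake.** Keep either type as the pre/post outcome in the segmented model. Report the two components separately, with IBT as a description of use of the covered benefit from 2012 on and not as a pre/post policy effect.
3. **Visit count.** Build the Section 8.0 predictor from the same flag, so that the visits counted are the visits defined.
4. **Aim 2 groups.** Make nutrition-only patients a category of their own, outside the uncounseled comparator.
5. **Weight outcome.** Replace or supplement the IBT-to-IBT definition in Table 1 with a weight change over a fixed calendar interval, taken from recorded EHR weights and defined alike for IBT, other-counseling and never-counseled patients. Moving the start to the first counseling visit of either type would not be enough, because the never-counseled would still have no value.

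The cost is one extra classification variable, a few more uptake curves, and revised wording in Section 1.0, Table 1 and Section 8.0. The documents do not say which counseling codes will be extracted, so the list must be agreed with the sites. No patient contact is needed.
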